Novel techniques have been developed as alternatives to conventional methods for caries removal in pediatric dentistry. The chemo-mechanical caries removal technique though it is more comfortable it requires more time with anticipation to conventional surgical methods for caries access and finishing the preparation (Soni et al., 2015). Several “chemo-mechanical caries removal agents” have been developed in the market since 1975. They can be generally categorized into either sodium hypochlorite (GK-101, GK-101E, Caridex®, Cariosolv®) (Fig.1) or enzyme-based agents (Papacárie®, Carie-Care™, Brix3000®) (Fig.2) (Hamama et al., 2014, Venkataraghavan et al., 2013, Felizardo et al., 2018).

Many investigations have compared the efficacy, time taken, and pain threshold of different chemo-mechanical agents versus the conventional surgical method.

Regarding the efficacy of caries removal, Goomer et al. (2013) concluded that chemo-mechanical method for removal of decay with Cariosolv was less effective than traditional surgical technique though it was a worthwhile alternative to the painful procedures; like drilling, especially among children, who are afraid of dentists. These results were confirmed by other studies conducted by “Pandit et al. (2007), Bohari et al. (2012) and Soni et al. (2015)”. Other studies conducted by “Fure et al. (2000), Banerjee et al. (2000), Bergmann et al. (2005), Lozano-Chourio et al. (2006), Peric et al. (2009) and Almaz et al. (2016), Kochhar et al. (2011)” showed that surgical and chemo-mechanical method exhibits similar efficacy to remove caries.

Maragakis et al. (2001) and Yazici et al. (2005) concluded that Cariosolv could not be an alternative to surgical method since the caries was not removed completely.

Regarding the time taken of caries removal, several studies found that chemo-mechanical methods needed significantly greater time compared to surgical caries removal. This is most likely because chemo-mechanical agents usually require frequent implementation for caries removal (Goomer et al., 2013, Soni et al., 2015, Banerjee et al., 2000, Pandit et al., 2007, Kochhar et al., 2011, Maragakis et al., 2001, Fure et al., 2000, Bergmann et al., 2005, Lozano-Chourio et al., 2006, Peric et al., 2009).

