- 2) To compare the efficiency of the chemo-mechanical method (BRIX3000[®], Carie-Care[™]) versus the conventional surgical method in caries removal of primary molar teeth in vivo.
- 3) To compare the pain experienced by children during dental treatment with the chemo-mechanical method (BRIX3000[®], Carie-Care[™]) versus the conventional surgical method in caries removal of primary molar teeth in vivo.

HYPOTHESIS

The null hypothesis for this research will be as follows:

There is no difference in the efficacy, efficiency and pain experienced between chemo-mechanical caries removal agents (Brix3000[®]), (Carie-CareTM) and the conventional surgical methods in primary molars.

RESEARCH MATERIALS AND METHODS

This study will be carried out at King Abdulaziz Dental University Hospital (KADUH) and at Microbiology Research Laboratory in the Faculty of Pharmacy, King Abdulaziz University in Jeddah, Saudi Arabia to evaluate the efficacy, efficiency, pain experienced by children with the use of the chemo-mechanical method (BRIX3000[®]) and (Carie-Care[™]) versus the conventional surgical method in primary molars.

Materials:

Ethical Approval

The study was approved by the “Research Ethics Committee” at Faculty of Dentistry, King Abdulaziz University (KAU), under approval number 107-06-19.

Informed Consent

Written informed consent will be received from the parents or the guardians of the children after explaining the research procedures to them.

Subjects (sampling)

The study sample will consist of healthy and cooperative children between the ages of 4-9 years with bilateral open occlusal carious lesions in primary molars, who will attend as outpatients to the Department of Pediatric Dentistry at KADUH during the period from October 2019 to October 2020.

Inclusion criteria:

- Healthy and cooperative patients of age group 4-9 years.
- Primary first/second molars with open occlusal carious lesion having moderated depth and clinically visible brownish color softened dentin.
- No clinical signs or symptoms of pulp degeneration, such as tenderness to percussion and history of sinus tracts or swelling. Intraoral periapical radiographs with lesions having radiolucency extending into, but only confined to dentin.

Exclusion Criteria:

- Patients with any major and minor systemic illness.
- Uncooperative patients that necessitate pharmacological dental treatment.

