- Primary molars with mobile teeth, arrested caries, restored teeth, non-vital teeth, no carious lesion, presence of developmental defects and non-restorable teeth.
- Patients on any antibiotic regimen either on the day of treatment or for at least 2 weeks prior to the study.
- Patients allergic to Latex.
- Radiographic evidence of external or internal root resorption, furcal or periapical radiolucency.
- Primary molars with more than half of the root length resorbed.
- Children who did not attend and complete the second session of treatment.
- Not approving to sign the consent.

Sample Size Calculation:

The sample size was measured using G power analysis for calculating estimated sample size.

Based on the results of Bohari et al. 2012, it was found that 30 subjects per group were required

to detect a statistically significant difference between the two groups anxiety score (FLACC) with a power of 95% at the significance level of 0.05.

The study group will be consisted of 120 primary molars with bilateral design from 60 children aged 4-9 years without sex predilection. The included teeth will be assigned randomly into one of the following groups according to the decay removal technique that will be utilized using two-arm parallel groups with split-mouth design:

The control group (A): (n=60) primary molars will be subjected to removal of caries using a conventional drilling method using carbide dental burs.

The test group (B): (n=30) primary molars will be subjected to removal of caries using a chemo-mechanical agent (Brix3000[®], Brix Medical Science, Carcarañá-Santa Fe, Argentina).

The test group (C): (n=30) primary molars will be subjected to removal of caries using a chemo-mechanical agent Carie-Care[™], Uni-Biotech Pharmaceuticals Private Limited, Chennai, India in collaboration with Vittal Mallya Scientific Research Foundation).

Armamentarium & Equipment

- 1) Basic dental examination Kit
- 2) Restorative kit
- 3) Brix3000[®] “Brix Medical Science, Carcarañá-Santa Fe, Argentina”
- 4) Carie-Care[™] “Uni-Biotech Pharmaceuticals Private Limited, Chennai, India in collaboration with Vittal Mallya Scientific Research Foundation”.
- 5) Dental bur “Low-Speed Tungsten Carbide round bur US-NO 1-8, Meisinger, USA. L.L.C., [name]; High-Speed Diamond round medium size 08-018, Meisinger, USA. L.L.C., [name]”

- 6) Rubber dam kit.
- 7) Sterile vial.
- 8) Bacteriological incubator

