The carious cavity will be treated with Carie-Care™ “Uni-Biotech Pharmaceuticals Private Limited, Chennai, India in collaboration with Vittal Mallya Scientific Research Foundation”. Following the instructions of the manufacturer, the Carie-Care™ gel will be brought to room temperature. The gel will be left in the carious lesion for 60 seconds. At that time, the appearance of the gel will be changed from translucent into cloudy. Then the gel will be removed with moistened cotton pellet and softened carious dentin will be scrapped off using spoon excavator ((Size #2, #3, #4; Nordent Manufacturing Inc., [name]). The process will be redone till consecutive administration of the gel was unsuccessful to turn into cloudy. Decay removal will be verified by probing with dental explorer (visual-tactile clinical criteria).

Statistical Analysis

The statistical assessment will be carried out using Statistical Package for Social Sciences (SPSS, V.20, IBM; Armonk, NY, USA). Analysis of data will be done through measuring *p*-value to determine statistical significance. The level of significance will be set at 0.05 (*p*-value of less than 0.05 was considered statistically significant). Various statistical methods will be used for measuring *p*-value depending whether the data will be normally distributed (parametric) or not normally distributed (non-parametric). For normally distributed data, paired sample t-test and independent sample t-test will be used. For non-normally distributed data, Wilcoxon signed rank test and Mann Whitney U test will be used.

Wong-Baker FACES® Pain Rating Scale

[figure not shown]

Figure 4: Wong-Baker FACES® Pain Rating Scale.

RESEARCH LIMITATIONS

Although, the chemo-mechanical methods cannot eliminate the dental caries completely, it tends to follow the principles of minimal intervention dentistry approaches. The generalization of results is one of the expected limitations of this research.

STRUCTURE OF THE RESEARCH

The research will be divided into several chapters:

- Chapter 1 will represent the introductory note on the state of dental caries among children and treatment approaches that are extensively used by the dentists including different chemo-mechanical agents used.
- Chapter 2 will present the literature review for the study.

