- Chapter 3 will depict the methodology for the research. It will provide in-depth explanation of the materials and methods used for gathering data regarding different treatment modalities used in this research.
- Chapter 4 will illustrate the results attained from this research.
- Chapter 5 will provide the discussion of findings on the basis of results obtained in the research.
- Chapter 6 will sum up the entire results with general conclusions, evaluation of hypothesis, policy implications, and recommendations.

THESIS PLAN

STEPS OF PhD THESIS	TIME FRAME (MONTH)											
	1	2	3	4	5	6	7	8	9	10	11	12
Application of CONSORT Statement 2010	X											
Proposal writing		X										
Proposal presentation			X									
Discussion with the statistician		X										
Ethical approval				X								
Registration					X							
Apply for funding					X	X						
Providing tools and materials							X					
Intervention for in-vivo study							X	X	X			
Intervention for in-vitro study							X	X	X			
Data analysis									X	X	X	
Thesis writing									X	X	X	
Thesis defense												X

EXPECTED FINDINGS

The findings may show an increased efficacy, efficiency with decreased pain experienced during caries removal of chemo-mechanical method using newly developed agent (Brix3000[®]) as the manufacturer company claimed compared to the previously-available (Carie-CareTM) and to the conventional surgical method. It may be recommended as an alternate treatment modality among children, who fear to visit clinics for getting dental treatments.

REFERENCES

Anusavice KJ, Kincheloe JE (1987). Comparison of pain associated with mechanical and chemomechanical removal of caries. J Dent Res.66:1680–1683.

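### One joint null over three outcomes is tested at an unadjusted 0.05 with no primary outcome, and the stated 95% power belongs to a score the trial does not measure

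*Combined protocol and SAP*

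**What the plan says.** The Hypothesis section gives one null: "There is no difference in the efficacy, efficiency and pain experienced between chemo-mechanical caries removal agents" and conventional drilling. It therefore spans three outcomes and three methods. Structure of the Research says how it will be used: "Chapter 6 will sum up the entire results with general conclusions, evaluation of hypothesis, policy implications, and recommendations".

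Clinical Procedures defines the outcomes as total viable count (TVC), removal time in seconds and the Wong-Baker FACES pain scale. None is called primary. The Research Objectives compare the two gels with drilling on each outcome. Expected Findings adds a gel-versus-gel question, anticipating better results for Brix3000 "as the manufacturer company claimed compared to the previously-available (Carie-CareTM) and to the conventional surgical method".

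Statistical Analysis states "The level of significance will be set at 0.05" and then names the tests: "For normally distributed data, paired sample t-test and independent sample t-test will be used", and for other data "Wilcoxon signed rank test and Mann Whitney U test will be used". It does not list contrasts, assign tests to them, adjust for multiplicity, plan confidence intervals or say what result would reject the joint null.

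Sample Size Calculation bases 30 subjects per group on detecting a difference "between the two groups anxiety score (FLACC) with a power of 95% at the significance level of 0.05".

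**The concern.** A single null over several outcomes and methods, tested piece by piece at 0.05, has no defined error rate unless the plan says which results count against it. If any one significant result is enough, the risk of a false rejection is well above 5%.

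The joint null can also be rejected for a reason unrelated to the main interest. The Literature Review reports that "several studies found that chemo-mechanical methods needed significantly greater time compared to surgical caries removal". A difference in time alone would then reject a hypothesis that also covers bacteria and pain, with no evidence on either. The document plans recommendations from this evaluation, so a reader needs to know which result the trial is meant to decide.

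The sample size does not settle the matter. FLACC is described there as an anxiety score and is not measured. Pain is measured on a different scale. The 95% power therefore attaches to none of the three trial outcomes.

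**Working it through.** **Inputs from the document.** Per-test level 0.05 (two-sided assumed, since sidedness is not stated). Three outcomes. 60 children in two parallel arms, each child contributing one drilled and one gel-treated molar, with 30 children per gel.

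**Inputs inferred or assumed.** The contrast count is inferred: 2 gels versus drilling × 3 outcomes = 6, plus gel versus gel × 3 outcomes = 3, total 9. Assumed: any single p<0.05 rejects the joint null, all nulls are true, and within-child and between-outcome correlations are each 0-0.7. The document gives no correlations.

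**The plan's own figure.** Thirty per group at 95% power cannot be reproduced, because no effect size or SD is given. Solving backwards with the noncentral t, n=30 and two-sided 0.05, it implies a standardised difference of d=0.947 for an independent test, or dz=0.681 for a paired test.

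**Independence reference.** The chance of at least one false rejection in k independent tests is 1 − 0.95^k:
- k=6: 1 − 0.95^6 = 0.265
- k=9: 1 − 0.95^9 = 0.370

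**Simulation of this design.** Paired t-tests for gel versus drill, independent t-tests for gel versus gel, 30 children per gel, 20,000 runs per setting.

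| Contrasts tested at 0.05 | Chance of at least one false rejection |
|---|---|
| Six gel vs drill | 0.21-0.27 |
| Nine, gel vs gel on within-child differences | 0.24-0.31 |
| Nine, gel vs gel on raw gel-tooth values | 0.27-0.36 |
| Six gel vs drill, between-outcome correlation 0.9 | about 0.16 |
| Four gel vs drill, bacteria and pain only | 0.16-0.19 |
| One outcome, two gel-vs-drill contrasts | 0.09-0.10 |
| One outcome, all three contrasts | 0.11-0.14 |
| One outcome, three contrasts with Holm | 0.04-0.05 |

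The row without time is the relevant one if the time nulls are false, as the Literature Review suggests.

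**Power after adjustment.** Holm's first step over three contrasts is 0.05/3 = 0.0167. At that level and n=30, the effects that had 95% power at 0.05 have power 0.881 (d=0.947) and 0.875 (dz=0.681). Detectable effects at 0.0167 are:
- 95% power: dz=0.78 paired, d=1.07 gel versus gel
- 80% power: dz=0.62 paired, d=0.86 gel versus gel

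Over nine contrasts the first step is 0.05/9 = 0.0056, and the same two powers become 0.780 and 0.761.

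**The case against.** The best defence is that the three objectives ask separate questions on different quantities, and separate questions need not share one error rate. That is a legitimate position. Read that way, the inflation is only 0.09-0.14 per outcome. But the document does not write three nulls. It writes one and plans to evaluate it. Even outcome by outcome, two or three contrasts at 0.05 exceed the nominal rate.

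A second defence is that the global null is implausible here. If time differs, the joint null is false and rejecting it is no error. The Literature Review also cites studies finding chemo-mechanical removal less painful; if the pain nulls against drilling are false too, the remaining bacterial pair gives only about 0.10. This stands, and it is why the larger figures are conditional. It does not help the plan, because a joint null that is expected to fail through time tells the reader nothing about bacteria.

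Third, the test mapping is largely implied: the design makes gel versus drill paired and gel versus gel independent, and the plan lists both kinds of test. That mostly stands. What stays open is whether gel versus gel uses raw values or within-child differences, and how the pre-removal count enters the bacterial comparison.

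A reader might also infer that the error is at least four times nominal, or that it reaches 37%. The documents support neither. The first depends on capping the assumed correlation at 0.7; at 0.9, six contrasts give about 0.16, roughly three times nominal. The second is the independence ceiling, and gel versus gel shares teeth or differences with the other contrasts, so the simulated maximum is about 0.36.

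**Conclusion.** The concern holds in a conditional form. Two facts need no assumption: the joint null has no primary outcome, rejection rule or multiplicity control, and the stated 95% power applies to no measured outcome.

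The size does depend on assumptions: an any-p<0.05 rule, all relevant nulls true, six to nine inferred contrasts, and correlations that the document does not give. On these, the false-rejection chance is about 0.21-0.27 for six contrasts and 0.24-0.36 for nine, lower if outcomes correlate above 0.7. It is about 0.16-0.19 for bacteria and pain against drilling if the time nulls are false. The plan should be changed before analysis. This is not a reason to doubt that the trial can be carried out.

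**What to change.** 1. In Hypothesis and Statistical Analysis, name one measured primary outcome, restate the null for that outcome only, and apply Holm across its three contrasts. Label the other two outcomes secondary, with no claim against the joint null. The restatement matters: if six unadjusted secondary contrasts may still reject the joint null, its error stays at about 0.20-0.30. If the joint null is kept, apply Holm across all nine contrasts.

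2. State that gel versus drill is a paired test within each agent's 30 children and gel versus gel is an independent test between children, using the tests already listed. For TVC, state one rule for the pre-removal count that covers the paired and the independent contrasts alike, and a rule for zero counts. Baseline adjustment of log10 TVC is optional, since its gain depends on an unknown correlation and on the zero-count rule.

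3. Report each contrast with a 95% confidence interval.

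4. In Sample Size Calculation, say that the 95% power refers to FLACC at an unadjusted 0.05 and does not carry over to the primary outcome. Give the effects that 30 children per agent can detect at 0.0167, as derived above, at both 95% and 80% power.

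**Cost.** Wording changes in three sections, with no extra children or data. A contrast with nominal 95% power has about 87-88% at Holm's first step (76-78% if all nine are covered), and the secondary outcomes lose confirmatory status.

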- 9) Inoculation loop.
- 10) Blood agar plates “Schaedler agar”
- 11) GC Fuji IX GP®.
- 12) A Stop Watch.

Methods:

Study design

Experimental, randomized controlled clinical trial with two-arm parallel groups and bilateral design following the “Consolidated Standards of Reporting Trials (CONSORT,2010)” statement (Fig.3).

Randomization

Since bilateral technique will be utilized in both parallel groups, it was decided to start on the right side irrespective of the method assigned by randomization. To control the variable of the side favored by the clinician, the researchers will make sure that each side is treated evenly by both methods using block randomization. Before recruiting participants, 60 sealed envelopes containing the randomization results will be arranged, sealed and mixed blindly in a box. Each envelope represents a block of the two contralateral teeth. The envelopes will be numbered blindly from 1 to 60. Each envelope will be opened immediately before starting the procedure on the right side.

[figure not shown]

Figure 3: Flow diagram of the Study

Clinical Procedures

The degree of dental destruction will be clinically determined by using a dental probe. Only open occlusal cavities with brown and softened dentin with broadly comparable depth exhibiting frank moderate cavitation will be chosen “severe decay, stage 5, ICDAS [International Caries Detection and Assessment System]” (Ismail et al., 2007, Dikmen, 2015). The depth of caries progression will be confirmed with an intraoral periapical radiograph such that radiolucency did not involve the pulp.

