To assess the efficacy of caries removal in all groups, the outer surface of the decayed lesion will be washed with sterile normal saline (5 mL) to avoid contamination of plaque bacteria before taking the sample. The first sample will be taken from superficial carious lesion with the aid of a sterile sharp spoon excavator (Size #4; Nordan Manufacturing Inc., [name]). After completing caries removal, the cavity will be washed with sterile normal saline (5 mL) and dried with a sterile cotton pellet. A second sample of dentin will be taken from different sites of the cavity including the walls and floor using a sterile sharp spoon excavator (Size #4; Nordan Manufacturing Inc., [name]). The first and second samples will be collected in screw cap sterile vials containing 1 ml of isotonic saline for microbiological evaluation. Following decay elimination by both techniques, cavities will be filled using Glass Ionomer restoration (GC Fuji IX GP[®]) according to manufacturer’s instructions. For Microbiological cultivation and evaluation, dentin samples of all groups will be processed in the Advanced Techniques Laboratory in Dental research within 2 hours of collection. The samples will be vortexed for 30 sec to remove the microorganisms from dentin. The samples will be then regularly watered to obtain a 10^4 , and a sterile loop full of sample (0.1 ml) will be collected and cultured with aseptic technique onto blood agar plates (Schaedler agar) by streaking method. Then, the plates will be incubated aerobically at 35°C for 24 hours. Using

colony counter, the total viable count (TVC) will be obtained and expressed as colony forming units “CFU” per ml of sample.

To determine the efficiency of caries removal in all groups, time will be recorded in seconds by using a stopwatch from the beginning of caries removal till the cavity is certain to be caries-free.

To assess the pain experienced throughout caries removal in all groups, the “Wong-Baker FACES® Pain Rating Scale” (Wong & Baker, 1988) will be utilized (Fig. 4).

Dental treatment will be accomplished according to the following steps:

- Local anesthesia will be used for all groups.
- Rubber dam isolation will be used for all groups.
- Caries removal will be done utilizing one of the 3 techniques as follows:

The Control Group: Caries removal using “conventional drilling method”

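### The analysis plan does not say how the pre-removal bacterial count enters the comparison of methods, names no adjustment for that count or for side/order, and plans p-values without confidence intervals

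*Combined protocol and SAP*

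**What the plan says.** All points are from the combined protocol and SAP.

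- **Statistical Analysis.** "Analysis of data will be done through measuring" the p-value, with significance at 0.05. The parametric tests are given as follows: "For normally distributed data, paired sample t-test and independent sample t-test will be used". Where normality fails, the signed rank and Mann-Whitney tests take their place. No test is tied to an outcome or a contrast. No covariate, side or order term, effect estimate or interval is mentioned.
- **Clinical Procedures.** In all groups, "The first sample will be taken from superficial carious lesion with the aid of a sterile sharp spoon excavator", and after removal, "A second sample of dentin will be taken from different sites of the cavity including the walls and floor". Both are cultured and counted.
- **Research Objectives.** The first objective is to compare methods in reducing cariogenic bacteria.
- **Randomization.** On order, "it was decided to start on the right side irrespective of the method assigned by randomization". On balance, the researchers will ensure that "each side is treated evenly by both methods using block randomization".
- **Exclusion Criteria.** One criterion reads "Children who did not attend and complete the second session of treatment", so the two teeth appear to be treated at separate sessions.
- **Sample Size Calculation.** There are 60 children and 120 molars: 60 drilled, 30 treated with Brix3000 and 30 with Carie-Care. Each child therefore supplies one drilled and one gel-treated tooth.

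**The concern.** The split-mouth layout largely implies which test serves which comparison: paired for drill against gel, independent for gel against gel. Three things remain open.

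1. **Pre-removal count.** The bacterial endpoint could be the post-removal count, the change, or a baseline-adjusted count. These differ in precision, and the choice could be made after the data are seen.
2. **Side and order.** The right tooth always comes first, so side and order are one factor, and session seems to coincide with it. The design balances method over this factor, but the analysis has no term for it. Any systematic right-left difference (learning, fatigue, anxiety at the second tooth) is counted as noise.
3. **Intervals.** The null hypothesis is no difference on three outcomes among three methods. A p-value above 0.05 does not show how large a difference is still compatible with 30 pairs, or with 30 against 30.

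**Working it through.** **The plan's own figure.** The stated 30 per group (95% power, 0.05, FLACC score) cannot be reproduced, because no mean difference or SD is given. Solving backwards, two-sided, it implies d = 0.95 for an independent t-test or 0.68 SD of the difference for a paired t-test. These concern FLACC, not bacterial counts.

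**Inputs.** From the documents: 30 pairs per gel, 30 against 30 for gel against gel, alpha 0.05. Assumed: unit SD; between-tooth correlation rb = 0.5; same-tooth pre/post correlation rp = 0.3, 0.5, 0.7; d = 0.5 for drill against gel; sides split 15/15 within each gel arm. The documents give none of the assumed values.

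**Unadjusted 95% half-widths.**
- Drill against gel: t(29) × √(2(1 − rb)/30) = 0.44, 0.37, 0.29 SD at rb = 0.3, 0.5, 0.7.
- Gel against gel: t(58) × √(2/30) = 0.52 SD.

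**Gel against gel, pre-removal count.** Relative to post-removal count alone, the variance is 1 − rp² with adjustment and 2(1 − rp) for a change score.

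| rp | Adjusted | Reduction | Change score | Adjusted half-width |
|---|---|---|---|---|
| 0.3 | 0.91 | 9% | 1.40 | 0.49 SD |
| 0.5 | 0.75 | 25% | 1.00 | 0.45 SD |
| 0.7 | 0.51 | 49% | 0.60 | 0.37 SD |

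**Drill against gel, pre-removal count.** What matters is the correlation between the within-child pre difference and post difference: ρ = (rp − c)/(1 − rb), where c is the correlation of one tooth's pre-count with the other tooth's post-count. Adjustment leaves variance 1 − ρ²; a change score leaves 2(1 − ρ). Since 2(1 − ρ) − (1 − ρ²) = (1 − ρ)² ≥ 0, adjustment never has the larger variance, before the small cost in degrees of freedom. At rb = 0.5:
- c = 0.5 rp (tooth-specific) gives ρ = rp.
- c = 0.75 rp gives ρ = 0.5 rp = 0.15, 0.25, 0.35.
- c = rp (a child-level trait) gives ρ = 0, because pairing has already removed it.

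Simulated power (20,000 runs; adjusted analysis = regression on the pre difference and a side term):

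| Source of pre/post correlation | Paired t, post count | Adjusted, rp = 0.3/0.5/0.7 | Paired t on change |
|---|---|---|---|
| Tooth-specific | 0.75 | 0.77/0.85/0.95 | 0.61/0.76/0.93 |
| Mixed (c = 0.75 rp) | 0.75–0.76 | 0.75/0.76/0.79 | 0.53/0.58/0.64 |
| Child-level | 0.75 | 0.74 throughout | 0.46–0.47 |

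With rp near zero the adjusted power is also about 0.74. Type I error of the regression stayed near 0.05 in all null settings.

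**Side/order term, no pre-count, d = 0.5.**

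| Right-left shift | Power without / with term | Type I error without / with term |
|---|---|---|
| 0.25 SD | 0.73 / 0.75 | 0.042 / 0.048 |
| 0.5 SD | 0.68 / 0.76 | 0.03 / 0.05 |

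If sides were only coin-tossed, a 0.5 SD shift gives power 0.66 / 0.74 and type I error 0.048 for both.

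**The case against.** The plan does not exclude the first sample. Its tests are tied to no outcome and could be run on the change in count, as the first objective suggests. That stands: a reader might infer that the pre-removal count is discarded, and the text shows only that its use is unspecified. The change score is also the weaker way to use it.

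The precision gain for drill against gel is not assured. If the pre/post correlation reflects a child's flora, pairing has already captured it and adjustment loses about 2 points. The first sample is superficial and the second comes from walls and floor, so a weak correlation is also possible. This stands; the rise to 0.95 is a best case. At the implied d = 0.95, drill-against-gel power is already 0.99 or more, and only the interval would narrow.

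Balance over sides already protects the planned tests, and the fix below leaves the face score without a side term for that reason. True. The term buys power, not validity, and only modestly. The unadjusted test is conservative only if sides are even within each gel arm, which the randomization text does not state explicitly.

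None of this touches the missing intervals, where the case needs no assumed correlation for gel against gel.

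**Conclusion.** The concern holds as one of precision and prespecification. The plan names no estimate or interval for any contrast, does not define how the pre-removal count is used, and has no term for the factor its own randomization balances.

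A reader might go further and infer bias from treating the right side first, or invalid tests. The documents do not support that: method is to be balanced over sides, and omitting the term does not inflate type I error.

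The missing intervals are the firmest element. For gel against gel, a non-significant result can coexist with a true difference of half an SD or more. Adjustment for the first count cuts that contrast's variance by 9% to 49% over the assumed correlations. For drill against gel, the effect runs from a loss of up to about 2 power points to a gain of about 20 (0.75 to 0.95). The side term recovers about 2 points at a 0.25 SD shift and 8 at 0.5 SD, given an even split within each gel arm. All effect sizes, correlations and shifts are assumptions.

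**What to change.** 1. **All contrasts.** Report an effect estimate with a 95% confidence interval, using Hodges-Lehmann for the rank tests. The face score can keep the signed rank and Mann-Whitney tests.
2. **Bacteria.** Prespecify log10 post-removal count adjusted for log10 pre-removal count, not a change score.
   - Drill against each gel: regress the within-child post difference on the within-child pre difference (uncentred) and a side/order term coded +1/−1; the intercept is the method effect.
   - Gel against gel: compare post-removal counts between children, adjusted for the tooth's pre-removal count and side.
   - Fix one value for zero counts in advance and keep the rank test as a sensitivity analysis.
3. **Time.** Analyse log seconds in pairs with the side/order term.

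The cost is wording in the analysis section; no extra children, samples or visits are needed. It uses one or two degrees of freedom and up to about 2 power points if the pre-count carries no within-child information. If the left tooth is first sampled at a second session, the adjustment assumes that treating one tooth does not alter the other's lesion, which the split-mouth design already assumes.
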